**b) To increase average length of cervical cytology testing among women under 30 years of age**

**Pre:** cervical cytology test interval among women who received two CC tests from same provider (analysis limited to providers who have been in program at least 36 months)

**Post:** cervical cytology test interval among women who received their second CC test 3-15 months after the intervention started.

**c)** To decrease the number of LEEP and cryotherapy procedures in women under 30 years of age with abnormal cytology.

**Pre:** Rate of women 21-29 years of age who receive LEEP or cryotherapy over total number of women 21-29 years of age in quarter before intervention started.

**Post:** Rate of women 21-29 years of age who receive colposcopy or LEEP or cryotherapy over total number of women 21-29 years of age in 3-6, 9-12, and 15-18 months after intervention started.

**d)** To decrease the number of colposcopy procedures in women 21-24 years of age with abnormal cytology.

**Pre:** Rate of women 21-24 years of age who receive colposcopy over total number of women 21-24 years in quarter before intervention started.

**Post:** Rate of women 21-24 years who receive colposcopy over total number of women 21-24 years of age in 3-6, 9-12, and 15-18 months after intervention started.

The primary outcome measure will compare the observed within-clinic changes in cervical cytology testing rates between intervention and comparison groups using a t-test accounting for clinic-level clustering. We will use the same approach to test differences between each of the APP and APP + PCA and the comparison groups. Tests will be adjusted for multiple comparisons. Secondary endpoints include examining the interval between tests for women who received two cervical cytology tests from the same provider and the decrease in the number (and percent) of women receiving colposcopy procedures and LEEP or cryotherapy procedures. These will be analyzed using a similar approach as adopted for the primary endpoint. Patient satisfaction surveys will be administered to all women evaluated and compared between interventions and the controls. Because most available data is on the clinic level, we will have limited opportunities to analyze patient-level data. However we will be able to conduct supplementary analyses to investigate the possible impacts of between-arm imbalances in clinic level characteristics such as racial/ethnic composition, age distribution, descriptors of lab procedures, additional app or educational materials that are not part of the assigned intervention, and cervical cancer screening educational activities. Prior to starting the intervention and during the study, administrators and physicians at each clinic site will be asked about possible confounding variables at their clinic.

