In addition, the 2006 consensus guidelines for management of abnormal cytology and histology were updated. For women under 26 years of age with abnormal cytology and histology, observation with cytology and colposcopy is recommended over invasive treatments such as LEEP and cryotherapy. More specifically, for young women with ASCUS and LSIL, it is recommended to repeat cytology annually and refer to colposcopy only if persistent at 2 years or if HSIL develops. Recommendations continue from the 2006 guidelines that young women with HSIL (CIN 2,3), defined as those interested in fertility, be followed by colposcopy and cytology rather than immediately referred for therapy.

Adherence to these screening and management guidelines has been disappointingly low, although the adherence to other national guidelines in general is low. Dissemination and implementation of these guidelines can be a challenge in the US--many women equate health care with annual Pap smears and continue to demand these examinations. In addition, many physicians may have financial incentives to over screen and treat or are not aware of current guidelines.

This research will be expected to influence adherence to guidelines and lead to improved patient health and well-being as this study would show interventions that are capable of lowering the number of unnecessary colposcopic examinations, cervical biopsies and excisional therapies. All of these procedures have been shown to have negative effects including psychological distress

and premature delivery. Numerous providers and stakeholders have underscored the need to avoid these unnecessary procedures.

There has been little done regarding physician based interventions regarding cervical cancer screening. In general, message based interventions (i.e., messages on laboratory reports), payment denials, and electronic medical record messages have all been examined with mixed results. Newer technologies have not been evaluated extensively in any setting. These include offering free applications (APPs) for mobile phones, which would give easy access to guidelines. In addition, no mobile application intervention for patient decision-making has been applied for cervical cancer screening.

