## **STUDY DESIGN**

### **Overview**

This is a clustered randomized trial with individual clinics serving as the clusters. Clinics from the California Family PACT provider network who serve at least 200 female clients per year <30 years of age will be randomized to one of 2 intervention arms: 1) physician based approach (APP), and 2) APP-based intervention plus patient-centered approach (PCA). We will reach out to eligible sites to identify which sites are willing to participate. Of these, we will randomize 14 clinics to one of the two intervention arms. These groups will be compared to a comparison group (those not randomized). Since Family PACT data is available for all sites, randomization is not necessary for the comparative groups. However, attention to size, cultural make-up and public versus private information will be accounted for in identifying 7 sites for comparison. Seven sites in each arm/group will result in an average of 2800-3500 women per arm/group—total of 8400-10500 women.

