**a) Decrease the rate of cervical cytology testing among women ages 21-29 years of age**

**Pre:** Rate of women 21-29 years of age who received cervical cytology tests over total number of women 21-29 years of age in quarter (3 months) before start of intervention

**Post:** Rate of women 21-29 years of age who received cervical cytology tests over total number of women 21-29 years of age in months 3-6, 9-12, and 15-18 after intervention started

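### Cytology at other Family PACT sites goes uncounted in outcome (a) and, on the stated endpoint, in outcome (b), so displaced tests can pass for less screening; (b) also words its provider rule differently for pre and post

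*Combined protocol and SAP*

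**What the plan says.** Outcome (b) under Data Analyses has two lines. The pre line takes the "cervical cytology test interval among women who received two CC tests from same provider", limited to providers at least 36 months in the program. The post line takes the "cervical cytology test interval among women who received their second CC test 3-15 months after the intervention started" and says nothing about the provider. The paragraph after outcome (d) applies the limit without separating the periods: "Secondary endpoints include examining the interval between tests for women who received two cervical cytology tests from the same provider".

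Outcome (a) is the number of women aged 21-29 who had cytology divided by all women of that age, in the quarter before start and in months 3-6, 9-12 and 15-18 after it. The Sample Size section calls these clinic-specific three-month rates, and the analysis paragraph states: "The primary outcome measure will compare the observed within-clinic changes in cervical cytology testing rates between intervention and comparison groups". Neither section says whether a test billed by another site counts, or whether the denominator is women seen in the quarter or a fixed panel.

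The Overview notes that the claims reach beyond the study clinics: "Since Family PACT data is available for all sites, randomization is not necessary for the comparative groups". The sensitivity section offers a leave-one-clinic-out jack-knife and analyses with and without patients who have missing data. Neither would show testing at other sites.

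**The concern.** The objective is how often women are screened, whereas the outcomes as written record how often one clinic bills for it. The two come apart if a woman deferred at an intervention clinic obtains the test at another site. The protocol gives grounds for expecting some of this. Screening and Management Guidelines says "many women equate health care with annual Pap smears and continue to demand these examinations", and the interventions aim to lengthen intervals to three years. Study Population lists 1,114 private and 456 public clinics in the study counties, of which only 14 receive an intervention. Clinic loyalty is not documented: the 74% retention figure refers to use of Family PACT, not of the same clinic.

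Comparison clinics receive no such push, so displacement could differ by arm. For outcome (a) it would look like reduced overscreening although the woman's exposure had not changed. Separately, the mismatch between the pre and post lines of (b) leaves open which tests form the post interval, and a programmer following the text literally would change the rule between periods.

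**Working it through.** There is no stated figure to reproduce: the plan gives no rate of cross-site testing, and the Sample Size section makes no power calculation for the interval. The inputs from that section are a 50% baseline rate, 430 women per clinic and a mean interval of 19 months. The share of tests elsewhere, s, the share of women moving and the SD of the interval are assumptions.

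**Outcome (a), woman still in the denominator.** With a clinic-specific numerator, the recorded rate is 50% x (1 - s):

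- s = 5%: 47.5%
- s = 10%: 45%
- s = 20%: 40%

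At s = 10%, 215 - 21.5 = 193.5 tests over 430 women is 45%. A woman deferred at a visit in that quarter has been seen, so she stays in the denominator even if it is visit-based.

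**Outcome (a), woman gone from the clinic.** If 43 of 430 women leave and the denominator is women seen, the rate is (215 - 21.5)/(430 - 43) = 193.5/387 = 50%, unchanged. With a fixed panel it is 193.5/430 = 45%.

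**Outcome (b), tested elsewhere and then returning.** With a constant s, the same-provider mean is 19/(1 - s): 20.0, 21.1 and 23.75 months at 5%, 10% and 20%. What matters for the comparison is a change in s after start, and the post interval is counted only if its second test falls in months 3-15. Let s be 10% before start, and 20% after it in the intervention arm only. If the SD equals the mean (19 months, exponential gaps), a home-clinic test at month t has an expected excess over the arm that stays at 10% of

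(19/0.8 - 19/0.9) x (1 - exp(-0.8t/19)) = 2.64 x (1 - exp(-0.0421t)).

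The average of exp(-0.0421t) over months 3 to 15 is (0.881 - 0.532)/(12 x 0.0421) = 0.692, so the excess is 2.64 x 0.308 = 0.81 months. With more regular testing it is smaller: simulation with gamma gaps gives about 0.14, 0.24 and 0.33 months at SDs of 6, 8 and 10.

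**Outcome (b), leaving for good.** Such a woman has no second same-provider test and contributes no interval. Simulation with SD 8 puts the mean among those left at 18.4 months if 10% move per year and 17.9 if 20% do. It shortens because long intervals are more often cut off.

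**Outcome (b), rule differing by period.** If pre is same-provider and post is any-provider, a stable 10% elsewhere gives 21.1 months before and 19.0 after, an apparent shortening of 2.1 months with no change in testing. It appears in every group. It largely cancels between groups if s is equal across them, but not in the within-arm comparisons that Data Analyses also plans.

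**The case against.** The strongest defence is that the interventions act on clinics, so a clinic's own testing is a legitimate target, and a test ordered by an untrained provider elsewhere says little about whether the app works. The analysis compares within-clinic changes between groups, so a stable level of cross-site testing largely cancels. The protocol says women ask for annual tests; it does not say they change clinics to get them. The patient tool is meant to make longer intervals acceptable, which argues against displacement in that arm. The interval is also a secondary, unpowered endpoint, and the plan warns that most of its data are at clinic level.

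Most of this stands, and it limits the point to displacement that differs by arm. It does not show that such displacement is absent, and no planned analysis would reveal it.

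A reader might infer more: that a rise from 10% to 20% elsewhere would add 23.75 - 21.1 = 2.6 months to the interval, and that any move to another clinic reads as a longer interval. The documents support neither. The 2.6 months applies the higher share to a woman's whole testing history, whereas the post window leaves at most 15 months for deferral, a test elsewhere and a return. A woman who leaves for good is dropped from (b), which is selection and, in the simulation above, slightly shortens the mean.

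**Conclusion.** The point holds in limited form. The provider rule for (b) is inconsistent between the pre and post lines and should be settled whatever one thinks about displacement. For (a), the primary outcome, displaced tests would overstate the reduction in proportion to the share displaced: 5 percentage points for an assumed 10%, provided the women stay in the denominator and tests at other sites are not credited, which is the natural reading but is not spelled out. For (b), the arm-differential distortion is about 0.1 to 0.8 months for an assumed rise from 10% to 20%, across assumed SDs of 6 to 19 months.

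It would go too far to say that the comparison is biased in favour of the intervention. That needs displacement to differ by arm, which is plausible from the protocol's own account but not measured. The change is worth making because the claims cover all sites, so the question can probably be checked.

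**What to change.** 1. State one provider rule for (b) and apply it to both pre and post.
2. For women seen at a study clinic in the window, add a version of (a) that counts cytology billed by any Family PACT provider in that window. State the denominator and the attribution rule for the clinic-specific version.
3. Add a version of (b) that takes the interval from a woman's cytology at the study clinic back to her most recent cytology at any Family PACT provider, before and after start.
4. Report both beside the clinic-specific versions and compare the gap between them by arm. A gap that widens more in the intervention arms than in the comparison group would indicate displacement.
5. First confirm that client identifiers link across sites. Outcome (b) already pairs tests within a woman, and Study Population lists client enrollment and claims databases, but the documents do not confirm cross-site linkage.

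The cost is claims programming and wording, with no new data collection if linkage exists. There are two downsides: tests elsewhere partly reflect untrained providers, which dilutes a pure provider effect, and tests paid outside the program stay unseen.

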## **Selection of Participants**

### *Inclusion Criteria*

#### Intervention arms:

We will identify Family PACT providers who meet the following inclusion criteria:

- Is located in one of the ten Southern California study counties
- Clinical care visits occurred to at least 200 women aged 21-29 years in FY 11/12
- Has a calculated average cytology interval of < 30 months (based on last 3 years)
- Cytology is sent to Quest laboratories

For comparison, we will select from the following:

- Is located in one of the ten Southern California study counties
- Clinical care visit occurred to at least 200 women aged 21-29 years in FY 11/12
- Has a calculated average cytology interval of < 30 months (based on last 3 years)
- Cytology is sent to Quest laboratories

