### **Sample Size Estimates and Power Calculations**

The database for FY 2010/11 shows that 386 clinics fit the criteria with 89 sites available for arms 1-2 and 297 available for the comparison group. The mean number of female clients aged 21-29 years seen at the eligible clinics was 560 and the mean number of cytology specimens, colposcopic examinations and LEEP/cryoprocures for this age group was 297, 40, and 4, respectively. In 2012, the mean cytology interval was 19 months. Very few clinics had an interval >30 months. There were no differences for any of the above variables between those

sites eligible for intervention and those for comparison. These numbers have not changed significantly in the past 2 years and will be updated for the baseline assessment.

After enrolling 7 sites into each arm, we estimate that we would have approximately 2800-3500 women aged 21-29 years in each arm. For each arm, baseline cytology rate in this age group would be approximately 50%, rate of colposcopy procedures for those who had cytology would be 13%, and rate of LEEP/cryotherapy procedures for those referred to colposcopy would be 10%.

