Parallel calculations for the secondary colposcopy outcome also are based on between-arm comparison of changes in three-month colposcopy rates from baseline levels, and assume that approximately 50% of women will receive cytology at baseline and follow-up in the control group, and that colposcopy rates will also remain unchanged at 13%. We also assume that the intervention-related reduction in cytology will result in approximately 20% fewer women eligible for colposcopy at follow-up. Based on similar assumptions about intracluster correlation and loss to follow-up, results indicate that with the planned total sample size of 9030, we will retain at least 80% power to detect an intervention-related reduction in colposcopy rate as small as 8% at the 5% (one-sided) significance level. Due to our conservative assumptions, we should have sufficient power to detect even smaller intervention-related effects in analyses adjusting for baseline characteristics.

We did not perform calculations for the testing interval length and LEEP outcomes because of the lack of preliminary data on their potential variability within and between clinics.

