### Data Analyses

Outcomes to be evaluated within and between intervention arms are based on the specific research aims:

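### Outcome (b) samples test intervals by different rules before and after the start and states no look-back, so the mean interval can shift with no change in practice

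*Combined protocol and SAP*

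**What the plan says.** All references are to the combined protocol and SAP.

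- **Data Analyses, outcome (b), pre:** "cervical cytology test interval among women who received two CC tests from same provider", with the restriction "analysis limited to providers who have been in program at least 36 months". No calendar window is set for the second test.
- **Data Analyses, outcome (b), post:** "cervical cytology test interval among women who received their second CC test 3-15 months after the intervention started". This is a 12-month window. The same-provider condition is not repeated here, although the later paragraph on secondary endpoints states it for the endpoint as a whole.
- **Look-back:** neither line says how far back the first test may lie.
- **Inclusion Criteria:** the baseline interval used for clinic eligibility is defined over three years: "Has a calculated average cytology interval of < 30 months (based on last 3 years".
- **Sample Size Estimates and Power Calculations:** "In 2012, the mean cytology interval was 19 months", without a sampling rule or a standard deviation. For power, "We did not perform calculations for the testing interval length and LEEP outcomes because of the lack of preliminary data".
- **Data Analyses, use of the outcome:** the section opens with "Outcomes to be evaluated within and between intervention arms". The primary analysis will "compare the observed within-clinic changes in cervical cytology testing rates between intervention and comparison groups", and the interval endpoint is to follow a similar approach.

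**The concern.** A change score is interpretable only if both halves measure the same thing. When both tests must fall inside a fixed stretch of history, long intervals are under-represented because they have fewer places to fit. When the second test falls in a later 12-month window and the first may lie anywhere earlier in the same claims history, those long intervals are counted. Outcomes (a) and (d) use the same measure before and after; outcome (b) does not.

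Longer screening intervals are a named study objective, so an artefact in that direction could pass for success. Under Progress Review, stakeholders see interim outcomes and may change the interventions, so a within-arm rise could influence decisions before the final comparison.

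**Working it through.** **The plan's own figure.** The 19-month mean is the only figure given for this outcome. It cannot be reproduced, because neither the sampling rule nor the variance is stated. What follows is therefore a range under assumptions.

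**Assumptions.** Gaps x between consecutive tests have density f(x). Testing is stationary and nothing changes at the start. The true mean is 19 months. The distribution is gamma, with lognormal as a check, and the coefficient of variation (CV) is 0.3 to 1.0. Distribution and CV are not in the documents.

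**Formula.** Observed mean = ∫ x·w(x)·f(x) dx / ∫ w(x)·f(x) dx, where w(x) is how readily a rule captures a gap of length x:

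- Pre, both tests within L months: w = max(L − x, 0).
- Post, second test in months 3-15, first test no earlier than month −L: w = 12 for x ≤ L + 3, then L + 15 − x, then 0 beyond L + 15. For L = 36 the look-back is 39 to 51 months.
- Fixed look-back K: w = 1 for x < K, otherwise 0.

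**Hand check, CV 1.0 (exponential), pre, L = 36.** exp(−36/19) = 0.1504.

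- Denominator: 19×36 − 361×0.8496 = 684 − 306.7 = 377.3.
- Numerator: 361×36×1.1504 − 2×6,859×0.8496 = 14,951 − 11,655 = 3,296.
- Mean: 3,296/377.3 = 8.7 months.

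**Pre period read as the last 36 months (gamma, months; rises from unrounded means).**

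| CV | Pre | Post, same claims start | Rise | Post, fixed 36-month look-back | Rise |
|---|---|---|---|---|---|
| 0.3 | 17.1 | 19.0 | 1.9 | 18.9 | 1.8 |
| 0.5 | 14.5 | 18.5 | 4.0 | 17.6 | 3.1 |
| 0.7 | 11.9 | 17.1 | 5.2 | 15.6 | 3.7 |
| 1.0 | 8.7 | 14.3 | 5.6 | 12.6 | 3.9 |

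Lognormal gaps give rises of 1.8 to 4.4 with the same claims start. The fixed-look-back columns show that the missing pre window produces a rise even without a longer post look-back.

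If the 19 months was itself obtained from pairs within 36 months, the true mean is longer and so is the shift. With lognormal gaps and CV 0.5, 19.0 becomes 25.2. The full range is 2.6 to 9.8, but its top end implies a true mean of 98.3 months and should carry little weight.

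**Other readings the text permits.**

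- 60 months of history, same start for both periods: rises of 0.8 (CV 0.3) to 5.2 (CV 1.0).
- 120 months of pre history, unlimited post look-back: 0.3 to 0.9 at CV 0.3 to 0.5, but still 3.5 at CV 1.0.
- 120 months of pre history, post look-back fixed at 36, CV 0.5: 18.1 to 17.6, a fall of 0.5.
- Both post tests required after the start, 36-month pre rule, CV 0.5: 14.5 to 8.4, a fall of 6.1.

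**Mirrored rules.** With a 12-month pre window and the same 39-51 month look-back, the shift is 0.0 in every scenario (for example 18.5 and 18.5 at CV 0.5).

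**Between groups (36-month reading, gamma, CV 0.5).**

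- True mean 17: 13.52 to 16.75, shift 3.23.
- True mean 21: 15.28 to 20.03, shift 4.75.
- Residual in the difference of changes: 4.75 − 3.23 = 1.52 months. With 60 months of history it is 2.74 − 1.67 = 1.07. With equal distributions it is 0.

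**The case against.** **The look-back is not in the text.** A reader might infer that the plan gives the post period a longer look-back and that the mean must therefore rise by months. Neither line states a look-back. The 36 months is a minimum for provider tenure, and the three-year period belongs to clinic eligibility. This objection stands: the 36-month reading is natural but inferred.

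**Claims probably reach further back.** The sample-size section uses FY 2010/11 data, Study Population describes retention over four years before FY 2012-13, and one ethics approval was still pending on 4/29/15. If the pre rule is also read as second tests in the last 12 months, with claims from month −60, the rise at a mean of 19 and CV 0.4 to 0.5 is only 0.0 to 0.2 months. This stands as a limit on size. It does not settle which reading an analyst would adopt.

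**The planned contrast removes most of it.** The endpoint compares changes between groups, and the sample-size section reports no difference in these variables, mean interval included, between the two eligible pools. The two intervention arms are randomized against each other. A reader might go the other way and infer that the between-group test is invalid; the documents do not support that. What remains is that the comparison clinics are not randomized against the intervention clinics and are matched on sector and size, not on interval. Similar pools do not guarantee similar groups of seven. Within-arm evaluation is announced, although no within-arm test is specified, and it has no such protection.

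**It is a secondary outcome without a power calculation.** True, and it limits the consequence.

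**Conclusion.** The defect holds in a conditional form. Outcome (b) builds one change score from two unlike sampling rules and fixes no look-back, so its shift under no change in practice depends in size and sign on how the analyst reads it. Under the 36-month reading the spurious rise is about 2 to 6 months against a 19-month baseline. With 60 months of history it is about 1 to 5; with very long history and CV up to 0.5 it is under 1 month; and some readings give a fall. All of this rests on assumed stationary gamma gaps with a true mean of 19 months.

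Within-arm changes are directly exposed. The between-group contrast is unbiased when interval distributions match and otherwise carries a residual of the order of 1.5 months for true means of 17 and 21. It would be wrong to conclude that a rise is certain or that the primary outcome is affected. The definition should be corrected before the outcome data are analysed.

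**What to change.** In Data Analyses, outcome (b), define both periods by one rule in all 21 clinics:

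- both tests from the same provider, stated for pre and post;
- second test in a 12-month window, for example months −15 to −3 before and 3 to 15 after the start;
- the same look-back before each second test, set as long as the claims history allows and clearly beyond 36 months.

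The last condition matters because the target interval is three years. With a 36-month look-back, a true change from 19 to 36 months would be recorded as 18.4 to 25.8 (gamma, CV 0.4) or 17.6 to 23.6 (CV 0.5), which is 7.4 or 6.0 of the 17 months. With 48 months it would be 18.9 to 30.8, or 18.7 to 28.5.

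**Cost.** The edit is short and needs no new data from clinics or patients. Claims must reach further back than the 36-month provider minimum: a 48-month look-back needs month −15 − 48 = −63, so the tenure restriction has to be aligned and clinics with shorter histories checked. Any finite common look-back still cuts off the longest intervals. It applies the same cut in both periods, so it creates no shift when practice is unchanged, but it understates a real lengthening.
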